9.3 Safety Analysis

The SAT Population will be the primary population for evaluating safety.

All subjects who receive at least one dose of study medication will be included in the summaries and listings of safety data. The overall safety profile and toleration of lorlatinib will be characterized by type, frequency, severity (as graded by CTCAE v5.0), timing and relationship of study treatment of AEs and laboratory abnormalities.

10. STUDY ORGANISATION AND COMMITTEES

10.1 Study Coordination

The study is an investigator-initiated, cooperative trial group trial.

10.2 Trial Management Committee

The Trial Management Committee will oversee study planning, monitoring, progress, review of information from related research, and implementation of recommendations from other study committees and external bodies (e.g. ethics committees).

Selection Bias: Real-world study population is relatively unselected compared with randomized clinical trials in terms of stringent inclusion and exclusion criteria.

However, selection bias still exists because the participants are not randomly drawn from the target population. First, patients will be recruited from particular sites that are characterized by the site's prevalent demographics, specific routine clinical practice procedures, and the different levels of experience in the investigators.

Second, there is also selection bias due to loss to follow up (also known as informative censoring), which often happen when a patient can no longer be tracked due to various reasons such as hospital referral or migration.

Information Bias: Information bias due to missing data exists in almost all kinds of studies. In contrast to the prospective clinical trials, where study variables are intentionally prespecified and collected, the availability, completeness of the data in this study requires special attention since the data is originally recorded without any intervention to prevent missingness.

Generalizability: While the real-world study can include a wider population than randomized control studies, the generalizability of this study may still be affected by the geographic location of the sample study population and hospital specific characteristics and may lead to differences in variations in outcomes. The analysis

will be done for each site to validate generalizability of outcomes respective of geographic location of the participants. Furthermore, disease assessment will be based on evaluations performed by the attending physicians in real-world clinical practice. Although a significant proportion of physicians use RECIST in their clinical practice, it may still result in an inconsistent definition of tumor response and disease progression. Such information bias can be minimized to some extent by following a well-designed data management process and through appropriated definition of variables to sufficiently use available information. Lastly, no hypotheses will be tested in this study and only descriptive analysis will be performed. Thus, results cannot serve as a general conclusion on the effectiveness and safety of lorlatinib.

11. QUALITY CONTROL AND QUALITY ASSURANCE

During study conduct, the Sponsor or its agent will conduct periodic monitoring visits to ensure that the protocol and Good Clinical Practice (GCP) are being followed. The monitors will review source documents to confirm that the data recorded on CRFs are accurate. The investigator and institution will allow Sponsor monitors or its agents and appropriate regulatory authorities direct access to source documents to perform this verification.

The study site may be subject to review by the Institutional Review Board (IRB)/Independent Ethics Committee (IEC), and/or to quality assurance audits performed by Sponsor or companies working with or on behalf of Sponsor, and/or to inspection by appropriate regulatory authorities.

It is important that the investigator(s) and their relevant personnel are available during the monitoring visits and possible audits or inspections, and that sufficient time is devoted to the process.

12. DATA HANDLING AND RECORD KEEPING

12.1 Case Report Forms/Electronic Data Record

As used in this study, the LinkDoc data management platform should be understood to refer to an electronic data record. Some of the sourced documents may be in paper format but whenever possible these should be transferred to an electron format.

The investigator has ultimate responsibility for the collection and reporting of all clinical, safety and laboratory data entered on the LinkDoc data management platform and ensuring that they are accurate, authentic/original, attributable, complete, consistent, legible, timely (contemporaneous), enduring and available when required.

In most cases, the source documents are the hospital's or the physician's subject chart. In these cases, data collected on the LinkDoc data management platform must match the data in those charts.

12.2 Record Retention

The records should be retained by the investigator according to International Conference on Harmonisation of Technical Requirements for Registration of Pharmaceuticals for Human Use (ICH), local regulations, or as specified in the Clinical Study Agreement, whichever dictates a longer period. If the investigator becomes unable for any reason to continue to retain study records for the required period (e.g., retirement, relocation), the Sponsor should be prospectively notified. The study records must be transferred to a designee acceptable to the Sponsor, such as another investigator, another institution, or to an independent third party arranged by the Sponsor. The investigator must obtain the Sponsor's written permission before disposing of any records, even if retention requirements have been met.

13. ETHICS

13.1 Institutional Review Board /Independent Ethics Committee

It is the responsibility of the investigator to have prospective approval of the study protocol, study amendments, informed consent forms, and other relevant documents (e.g., recruitment advertisements), if applicable, from the IRB/IEC. All correspondence with the IRB/IEC should be retained in the Investigator File. Copies of IRB/IEC approvals should be forwarded to the Sponsor.

The only circumstance in which an amendment may be initiated prior to IRB/IEC approval is where the change is necessary to eliminate apparent immediate hazards to the subjects. In that event, the investigator must notify the IRB/IEC and Sponsor in writing immediately after the implementation.

13.2 Ethical Conduct of the Study

The study will be conducted in accordance with legal and regulatory requirements, as well as the general principles set forth in the International Ethical Guidelines for Biomedical Research Involving Human Subjects (Council for International Organizations of Medical Sciences 2002), and the Declaration of Helsinki (World Medical Association 1996 and 2008).

In addition, the study will be conducted in accordance with the protocol, the ICH guideline on GCP, and applicable local regulatory requirements and laws.

13.3 Subject Information and Consent

All parties will ensure protection of subject personal data and will not include subject names on any Sponsor forms, reports, publications, or in any other disclosures, except where required by law.

Subject names, address, birth date and other identifiable data will be replaced by an alphanumeric code consisting of a numbering system provided by the Sponsor. In case of data transfer, the Sponsor will maintain high standards of confidentiality and protection of subject personal data.

The informed consent form must be in compliance with ICH GCP, local regulatory requirements, and legal requirements.

The informed consent form used in this study, and any changes made during the course of the study, must be prospectively approved by both the IRB/IEC and the Sponsor before use.

The investigator must ensure that each study subject, or his/her legally acceptable representative, is fully informed about the nature and objectives of the study and possible risks associated with participation. The investigator, or a person designated by the investigator, will obtain written informed consent from each subject or the subject's legally acceptable representative before any study-specific activity is performed. The investigator will retain the original of each subject's signed consent form.

13.4 Subject Recruitment

Advertisements approved by IRB/IEC and investigator databases may be used as recruitment procedures.

13.5 Reporting of Safety Issues and Serious Breaches of the Protocol or ICH GCP

In the event of any prohibition or restriction imposed (i.e., clinical hold) by an applicable Competent Authority in any area of the world, or if the investigator is aware of any new information which might influence the evaluation of the benefits and risks of the investigational product, the Sponsor should be informed immediately.

In addition, the investigator will inform the Sponsor immediately of any urgent safety measures taken by the investigator to protect the study subjects against any immediate hazard, and of any serious breaches of this protocol or of ICH GCP of which the investigator becomes aware.

14. PUBLICATION OF STUDY RESULTS

Publication of study results is discussed in the Clinical Study Agreement.

14.1 Communication of Results by the Sponsor

The Sponsor shall fulfill its commitment to publicly disclose clinical study results through posting the results of this study on www.clinicaltrials.gov (ClinicalTrials.gov).

14.2 Publications by Investigators

The investigator will, on request, remove any previously undisclosed confidential information (other than the study results themselves) before disclosure.

The investigator agrees that the first publication is to be a joint publication covering all centers. However, if a joint manuscript has not been submitted for publication within 12 months of completion or termination of the study at all participating sites, the investigator is free to publish separately, subject to the other requirements of this section.

For all publications relating to the study, the institution will comply with recognized ethical standards concerning publications and authorship, including Section II - "Ethical Considerations in the Conduct and Reporting of Research" of the Uniform Requirements for Manuscripts Submitted to Biomedical Journals,

<http://www.icmje.org/index.html#authorship>, established by the International Committee of Medical Journal Editors.

Publication of study results is defined in the Clinical Study Agreement between the Sponsor and the institution. In this section, entitled Publications by Investigators, the defined terms shall have the meanings given to them in the Clinical Study Agreement.

APPENDIX 1 ECOG Performance Status

Grade	ECOG
0	Fully active, able to carry on all pre-disease performance without restriction.
1	Restricted in physically strenuous activity but ambulatory and able to carry out work of a light or sedentary nature, e.g., light house work, office work.
2	Ambulatory and capable of all self-care but unable to carry out any work activities. Up and about more than 50% of waking hours.
3	Capable of only limited self-care, confined to bed or chair more than 50% of waking hours.
4	Completely disabled. Cannot carry on any self-care. Totally confined to bed or chair.
5	Dead.

APPENDIX 2 Medications with Potential PR Interval Prolongation

Effect

Note that the drugs listed below are examples and this is not intended to be an all-inclusive listing

Electrophysiologic Effects of Select Drugs on PR Interval Based on Product Labeling		
Drug	Action	Indications
Affecting AV nodal conduction (PR interval)		
Adenosine	Adenosine receptor	PSVT
Amiodarone	Cardiac ion channels	Antiarrhythmics
Disopyramide		
Encainide		
Flecainide		
Moricizine		
Propafenone		
Verapamil		
Arsenic trioxide	Multiple actions	Acute promyelocytic Leukemia
Atazanavir	HIV-protease inhibitors	Antiretroviral inhibitor
Lopinavir/Ritonavir		
Saquinavir		
Digoxin	Multiple actions	Congestive heart failure
Dolasetron	5HT3 receptor antagonist	Antiemetic
Fingolimod	S1P receptor modulator	Multiple sclerosis
Lacosamide	Not fully characterized	Partial-onset seizures
Pregabalin	Not fully characterized	Neuropathic pain
Mefloquine	Plasmodicidal effects	Antimalarial

Drugs were initially screened using the PDR3D database for PR interval prolongation using terms “PR interval prolongation”, “AV block”, “AV conduction delay”, or “heart block”. Drugs were subsequently selected for inclusion on the basis on descriptions of PR interval prolongation/AVB contained with Warning or Precautions sections of drug labels.
 
PSVT, Paroxysmal supraventricular tachycardia.
		

APPENDIX 3 RECIST Version 1.1

Adapted from E.A. Eisenhauer, et al: New response evaluation criteria in solid tumors: Revised RECIST guideline (version 1.1). European Journal of Cancer 45 (2009) 228–247.

CATEGORIZING LESIONS AT BASELINE

Measurable Lesions

Lesions that can be accurately measured in at least one dimension.

Lesions with longest diameter twice the slice thickness and at least 10 mm or greater when assessed by CT or MRI (slice thickness 5-8 mm)

Lesions with longest diameter at least 20 mm when assessed by Chest X-ray

Superficial lesions with longest diameter 10 mm or greater when assessed by caliper

Malignant lymph nodes with the short axis 15 mm or greater when assessed by CT.

NOTE: The shortest axis is used as the diameter for malignant lymph nodes, longest axis for all other measurable lesions.

Non-measurable disease

Non-measurable disease includes lesions too small to be considered measurable (including nodes with short axis between 10 and 14.9 mm) and truly non-measurable disease such as pleural or pericardial effusions, ascites, inflammatory breast disease, leptomeningeal disease, lymphangitic involvement of skin or lung, clinical lesions that cannot be accurately measured with calipers, abdominal masses identified by physical exam that are not measurable by reproducible imaging techniques.

Bone disease: Bone disease is non-measurable with the exception of soft tissue components that can be evaluated by CT or MRI and meet the definition of measurability at baseline.

Previous local treatment: A previously irradiated lesion (or lesion subjected to other local treatment) is non-measurable unless it has progressed since completion of treatment.

Normal sites

Cystic lesions: Simple cysts should not be considered as malignant lesions and should not be recorded either as target or non-target disease. Cystic lesions thought to represent cystic metastases can be measurable lesions, if they meet the specific definition above. If non-cystic lesions are also present, these are preferred as target lesions.

Normal nodes: Nodes with short axis <10 mm are considered normal and should not be recorded or followed either as measurable or non-measurable disease.

RECORDING TUMOR ASSESSMENTS

All sites of disease must be assessed at baseline. Baseline assessments should be done as close as possible prior to study start. For an adequate baseline assessment, all required scans must be done within 28 days prior to treatment and all disease must be documented appropriately. If baseline assessment is inadequate, subsequent statuses generally should be indeterminate.

Target lesions

All measurable lesions up to a maximum of 2 lesions per organ, 5 lesions in total, representative of all involved organs, should be identified as target lesions at baseline. Target lesions should be selected on the basis of size (longest lesions) and suitability for accurate repeated measurements. Record the longest diameter for each lesion, except in the case of pathological lymph nodes for which the short axis should be recorded. The sum of the diameters (longest for non-nodal lesions, short axis for nodal lesions) for all target lesions at baseline will be the basis for comparison to assessments performed on study.

If two target lesions coalesce the measurement of the coalesced mass is used. If a large target lesion splits, the sum of the parts is used.

Measurements for target lesions that become small should continue to be recorded. If a target lesion becomes too small to measure, 0 mm should be recorded if the lesion is considered to have disappeared; otherwise a default value of 5 mm should be recorded.

Non-target disease

All non-measurable disease is non-target. All measurable lesions not identified as target lesions are also included as non-target disease. Measurements are not required but rather assessments will be expressed as ABSENT, INDETERMINATE, PRESENT/NOT INCREASED, INCREASED. Multiple non-target lesions in one organ may be recorded as a single item on the case report form (e.g. 'multiple enlarged pelvic lymph nodes' or 'multiple liver metastases').

OBJECTIVE RESPONSE STATUS AT EACH EVALUATION

Disease sites must be assessed using the same technique as baseline, including consistent administration of contrast and timing of scanning. If a change needs to be made the case must be discussed with the radiologist to determine if substitution is possible. If not, subsequent objective statuses are indeterminate.

Target disease

Complete Response (CR): Complete disappearance of all target lesions with the exception of nodal disease. All target nodes must decrease to normal size (short axis < 10 mm). All target lesions must be assessed.

Partial Response (PR): Greater than or equal to 30% decrease under baseline of the sum of diameters of all target measurable lesions. The short diameter is used in the sum for target nodes, while the longest diameter is used in the sum for all other target lesions. All target lesions must be assessed.

Stable Disease (SD): Does not qualify for CR, PR or Progression. All target lesions must be assessed. Stable can follow PR only in the rare case that the sum increases by less than 20% from the nadir, but enough that a previously documented 30% decrease no longer holds.

Progression Disease (PD): 20% increase in the sum of diameters of target measurable lesions above the smallest sum observed (over baseline if no decrease in the sum is observed during therapy), with a minimum absolute increase of 5 mm.

Indeterminate: Progression has not been documented, and

one or more target measurable lesions have not been assessed

or assessment methods used were inconsistent with those used at baseline

or one or more target lesions cannot be measured accurately (e.g., poorly visible unless due to being too small to measure)

or one or more target lesions were excised or irradiated and have not reappeared or increased.

Non-target disease

CR: Disappearance of all non-target lesions and normalization of tumor marker levels. All lymph nodes must be 'normal' in size (<10 mm short axis).

Non-CR/Non-PD: Persistence of any non-target lesions and/or tumor marker level above the normal limits.

PD: Unequivocal progression of pre-existing lesions. Generally the overall tumor burden must increase sufficiently to merit discontinuation of therapy. In the presence of SD or PR in target disease, progression due to unequivocal increase in non-target disease should be rare.

Indeterminate: Progression has not been determined and one or more non-target sites were not assessed or assessment methods were inconsistent with those used at baseline.

New Lesions

The appearance of any new unequivocal malignant lesion indicates PD. If a new lesion is equivocal, for example due to its small size, continued assessment will clarify the etiology. If repeat assessments confirm the lesion, then progression should be recorded on the date of the initial assessment. A lesion identified in an area not previously scanned will be considered a new lesion.

Subjective Progression

Subjects requiring discontinuation of treatment without objective evidence of disease progression should not be reported as PD on tumor assessment CRFs. This should be indicated on the end of treatment CRF as discontinuation due to Global Deterioration of Health Status. Every effort should be made to document objective progression even after discontinuation of treatment.

Table 1. Objective Response Status at Each Evaluation

Target Lesions	Non-target Disease	New Lesions	Objective status
CR	CR	No	CR
CR	Non-CR/Non-PD	No	PR
CR	Indeterminate or Missing	No	PR
PR	Non-CR/Non-PD, Indeterminate, or Missing	No	PR
SD	Non-CR/Non-PD, Indeterminate, or Missing	No	Stable
Indeterminate or Missing	Non-PD	No	Indeterminate
PD	Any	Yes or No	PD
Any	PD	Yes or No	PD
Any	Any	Yes	PD

If the protocol allows enrollment of patients with only non-target disease, the following table will be used:

Table 2. Objective Response Status at each Evaluation for Patients with Non-Target Disease Only

Non-target Disease	New Lesions	Objective status
CR	No	CR
Non-CR/Non-PD	No	Non-CR/Non-PD
Indeterminate	No	Indeterminate
Unequivocal progression	Yes or No	PD
Any	Yes	PD

Best Overall Response

The best overall response (BOR) is the best response recorded from the start of treatment until disease progression. This is derived from the sequence of objective statuses. Objective statuses are not considered after objective progression is documented or after start of the first anticancer treatment post discontinuation of protocol treatment. BOR for each patient will be derived as one of the following categories.

Complete Response (CR): At least one objective status of CR documented before progression.

Partial Response (PR): At least one objective status of PR documented before progression.

Stable Disease (SD): At least one objective status of stable documented at least 8 weeks after start of treatment date and before progression but not qualifying as CR, PR.

Progressive Disease (PD): Objective status of progression within 12 weeks of start of treatment date, not qualifying as CR, PR or SD.

Indeterminate (IND): Progression not documented within 12 weeks after start of treatment date and no other response category applies.

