After lorlatinib treatment for 4 weeks, patients will receive an imaging assess. The patients who achieve PR or SD with oligometastasis (refer to target lesions with residual disease, a maximum of 3 organs, and no more than 5 lesions in total) should continue lorlatinib treatment and will receive imaging assess per 8-12 weeks. If target lesions indicate stable in 2 consecutive imaging, investigators will organize MDT and comprehensively evaluate patients' will to decide and choose local therapy. The local therapy includes surgery, ablation and, radiotherapy et al. After local therapy, patients should continue taking lorlatinib. While those who achieve CR or with multiple metastasis will continue lorlatinib treatment without any local therapy.

To dynamically monitor ctDNA changes in ALK + NSCLC patients during Lorlatinib treatment; to explore the correlation between ctDNA and Lorlatinib treatment efficacy .Patients need check the ctDNA-seq (10000x) in plamsa with NGS at baseline,4weeks after lorlatinib treatment and at disease progression.

Subjects will be on lorlatinib therapy until disease progression or unacceptable toxicity, new systemic anticancer therapy instituted, withdrawal of consent, death, or investigator decision dictated by protocol compliance, whichever occurs first.

Patients received continuous daily PO dosing of lorlatinib 100mg QD with/without locally therapy, from the date of first dosing (per the current protocol) or until one of the following criteria were met (whichever occurred first): disease progression; initiation of a new anti-cancer therapy; unacceptable toxicities; global deterioration of health-related symptoms; pregnancy; withdrawal of consent; loss to follow-up; death; investigator decision dictated by protocol non-compliance; or study termination. Patients who have progressive disease (PD) (per RECIST v1.1, by investigator review) and for whom the investigator believes it is in their best interest to continue lorlatinib treatment are allowed to continue lorlatinib therapy, at the discretion of the investigator, until any alternate or additional systemic anti-cancer therapy regimen was implemented.

At the time of progression and termination of study treatment, the patients could receive

any therapy at the judgment of the investigator. This study will take 1 years to enroll subjects, and each subject will be followed up for survival status and subsequent cancer therapies up to 60 months from the date of first dosing.

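### Appendix 3 does not cover ablated target lesions, enlarged treatment zones or locally treated non-target lesions, so the procedure itself can be scored as response or progression

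*Protocol*

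**What the plan says.** Section 3.1 sets out the treatment mode under study: "The local therapy includes surgery, ablation and, radiotherapy et al". Section 5.1 repeats this. Response continues to be scored after the procedure, because "After local therapy, patients should continue taking lorlatinib". Section 7.2.1 makes Appendix 3 the scoring standard.

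Appendix 3 deals with local treatment in two places.

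- **Baseline categorisation:** "A previously irradiated lesion (or lesion subjected to other local treatment) is non-measurable unless it has progressed since completion of treatment". This reaches any local treatment, but it decides which lesions count as measurable at entry.
- **On-study target disease, Indeterminate:** "or one or more target lesions were excised or irradiated and have not reappeared or increased". This names two modalities and carries a condition on reappearance or increase. The whole Indeterminate category applies only where progression has not been documented.

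The non-target section has no local-treatment clause. Its CR rule is "CR: Disappearance of all non-target lesions and normalization of tumor marker levels", plus normal lymph node size. Its Indeterminate rule is limited to undetermined progression where "one or more non-target sites were not assessed or assessment methods were inconsistent with those used at baseline".

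For a target lesion that is no longer seen, the recording rule is that "0 mm should be recorded if the lesion is considered to have disappeared".

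**The concern.** Ablation is one of three named local therapies, yet the on-study clause omits it. An ablated target lesion is therefore scored as if untreated: its disappearance counts as shrinkage, and a treatment zone wider than the lesion counts as growth. The second problem also affects irradiated lesions, because a lesion that measures larger has increased and so falls outside the clause. A non-target lesion that was resected or ablated simply counts as having disappeared.

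These errors can arise only in locally treated patients, the group the study is about. They enter investigator-assessed ORR, DOR, TTP and progression pattern (section 2.2), where an effect of the procedure would be read as an effect of lorlatinib or as failure of it. The status is recorded at site, so a later analysis rule could repair it only in part.

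**Working it through.** The protocol states no figure on this point, so there is nothing to reproduce. The check runs assumed lesion sizes through the Appendix 3 rules as written.

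**Rules.** Let B be the baseline sum, N the smallest sum so far and S the current sum.

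- PR: (B - S)/B is at least 30%.
- PD: (S - N)/N is at least 20% and S - N is at least 5 mm.
- Target CR: all target lesions gone (non-nodal lesions assumed here).
- Overall status: Appendix 3, Table 1.

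**1. Ablated target recorded as 0 mm, starting from SD.** B = 50 and S = 40, so (50 - 40)/50 = 20%: SD. One 20 mm lesion is ablated and recorded as 0, so S = 20 and (50 - 20)/50 = 60%: PR. The same lesion excised, or irradiated without enlargement: Indeterminate.

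**2. Ablated target recorded as 0 mm, starting from PR.** A single target goes from 30 to 15 mm: (30 - 15)/30 = 50%, PR. Ablated and recorded as 0: target CR, and overall CR if non-target status is CR.

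**3. Treatment zone larger than the lesion.** N = 20 + 20 = 40. One zone measures 30 mm, so S = 50, S - N = 10 mm and 10/40 = 25%: PD. This holds after ablation, and equally after radiotherapy, because the lesion has increased and progression is documented. In general, a zone wider than the lesion by g gives PD when g is at least the larger of 5 mm and 0.2 x N. For g = 10 mm this means N up to 10/0.2 = 50 mm; for g = 20 mm, N up to 20/0.2 = 100 mm.

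**4. Last non-target lesion removed.**

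| Target status | Overall before removal | Overall after removal |
|---|---|---|
| CR | PR | CR |
| PR | PR | PR |
| SD | Stable | Stable |
| Indeterminate | Indeterminate | Indeterminate |

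Table 1 has no explicit row for target PR or SD with non-target CR; these are taken as PR and Stable. Only the first row changes, from one responder category to another, so ORR does not move.

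**Cases 1 and 3 are alternatives.** If the zone in case 1 measured 30 mm at the next scan, the sum would go from 40 to 50 mm (+25%, +10 mm): PD. Appendix 3 disregards statuses after documented progression, so a later 0 mm could no longer produce a PR. The two effects cannot be added for one patient.

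**With the fix below:** cases 1 and 2 become Indeterminate, so the earlier SD or PR remains the best status recorded. Case 3 is Indeterminate unless there is growth beyond the first post-procedure scan. Case 4 stays PR, since Table 1 gives PR for target CR with non-target Indeterminate.

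**The case against.** **Other text may fill the gap.** Appendix 3 also makes a target status Indeterminate if "or one or more target lesions cannot be measured accurately (e.g., poorly visible unless due to being too small to measure" applies. A reader may well use this for tumour inside an ablation zone. That stands in part, but it is discretionary, and neither a lesion recorded as 0 mm nor a sharply bounded zone clearly qualifies.

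**The best-response window may already close.** Section 9.2.4 stops counting at the start of other anticancer therapy. If local therapy counts, procedure-made PR and CR drop out of ORR. But 9.2.4 does not say so, section 5.1 treats local therapy as part of the therapeutic mode, and Appendix 3 cuts off only at anticancer treatment begun after protocol treatment has stopped. False PD would remain under either reading.

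**Reach is limited.** This stands. The primary endpoint is time to lorlatinib discontinuation (section 9.2.2). Progression is a stopping criterion, but section 3.1 allows treatment beyond it. Section 3.1 assigns RANO-BM to intracranial lesions in patients with brain metastases. The analyses are described as descriptive, and inconsistent response definition is an acknowledged limitation (section 10.2).

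**Stronger readings that the documents do not support.**

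- A reader might infer that ablation yields false PD where radiotherapy would not. At the same enlarged measurement both score PD; the contrast holds only against excision, or where the irradiated lesion did not enlarge.
- A reader might infer that resecting non-target lesions inflates ORR. Case 4 shows that it cannot. Non-target PD needs unequivocal progression, so a procedure-made PD there is remote.
- A reader might put a range on the ORR inflation. Assuming 10-20% SD, 50-100% of these locally treated and 20-40% of those ablated gives 0.10 x 0.50 x 0.20 = 1 point to 0.20 x 1.00 x 0.40 = 8 points. None of these shares is in the protocol, and the product also assumes that every ablated patient had a target lesion treated and crossed the 30% threshold. The true lower end is near zero.

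**Conclusion.** The point holds as a defect in a stated scoring rule. Appendix 3 covers two of the three named local therapies for target lesions, removes that cover when the treated lesion measures larger, and has no rule for treated non-target lesions. Followed literally, it can record a procedure as PR, CR or PD.

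The exposed results are secondary: ORR through ablated target lesions only, any reported CR rate, DOR, TTP and progression pattern, mainly for extracranial disease. TTD is affected only if a procedure-made PD leads to stopping lorlatinib.

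The lesion sizes above are assumptions that show the mechanism. The protocol gives neither lesion sizes nor the share of patients ablated, so no magnitude can be stated. The correction is still worth making, because the errors fall selectively on the locally treated patients and the change is cheap.

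**What to change.** 1. **Target disease, Indeterminate (Appendix 3).** Extend the clause to lesions excised, irradiated, ablated or otherwise locally treated.
2. **Meaning of increased.** For every modality, define it as growth relative to the first post-procedure scan, and apply the same reference in the PD rule so that the treatment zone itself is not progression. Adding ablation to the list alone would leave case 3 at PD.
3. **Non-target disease.** State that a locally treated lesion cannot contribute to CR and makes non-target status Indeterminate (overall PR with target CR, by Table 1) unless it reappears or unequivocally grows.
4. **Best-response window.** State in section 9.2.4 and in Appendix 3, in the same terms, whether local therapy given while lorlatinib continues ends the window.

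The cost is a few sentences, plus recording the date, type and treated lesion for each local procedure. The downside is slightly fewer CR and PR and more Indeterminate assessments after local therapy, so the number of Indeterminate assessments should be reported beside ORR, DOR and TTP.
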